3.10 Randomization

There will be no randomization or allocation concealment.

3.11 Blindness

There will be no blindness at the level of the patient, the treating physicians (surgeon, oncologist, radiotherapist) and the researcher who will record the data.

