2. OBJECTIVE

2.1 Description of the proposed project

The objective of this study is the evaluation of different imaging methods for the optimal preoperative staging of colon cancer patients. Imaging findings will be compared with the histopathologic results of the specimen following surgical resection.

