3.4 Study Arms

In this study there will be one arm. All prospectively included patients with colon cancer will be preoperatively submitted to MRI for staging. The evaluation of the diagnostic accuracy will be based on the cross-examination with the CT scan and the pathology results.

The MRI protocol will include the following imaging series: T1 and T2 in axial and coronal plane before the administration of intravenous contrast, diffuse weight imaging in axial plane and T1 after the administration of intravenous contrast.

The CT scan protocol will include the following: per os and intravenous administration of contrast, axial slices of 0.3mm thickness and reconstruction per 1mm, multi-planar reformation and three-dimensional volume rendering.

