3.13 Monitoring

Following hospital discharge, the patient will be called for reassessment at one month after the operation. Patients will be included in the standard monitoring protocol (CT, MRI, cancer markers),

unless otherwise required. At the same time, the pathological assessment of the specimen will be recorded.

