3.15 Study Group

All participating members have years of experience in their field and have, therefore, completed the learning curve for the required techniques. Data collection and recording will be carried out by an independent, third party, researcher.

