3.16 Conducting a Study

The study will be conducted in the Department of Surgery of University Hospital of Larissa in collaboration with the Radiology Department of University Hospital. Patient data will be recorded

both in the patient charts and in an electronic database. The required laboratory examinations will be defrayed by the patient insurance funds.

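### Protocol 3.11 does not provide for the pathologist, who supplies the main reference standard, to be masked to the preoperative MRI

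*Protocol*

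**What the plan says.** Section 3.11 lists who is not masked: "There will be no blindness at the level of the patient, the treating physicians (surgeon, oncologist, radiotherapist", followed by "and the researcher who will record the data". Neither the pathologist nor the radiologists appear in the list, and no other section deals with masking.

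Section 2.1 sets the reference: "Imaging findings will be compared with the histopathologic results of the specimen following surgical resection". Section 3.4 repeats it with an addition: "The evaluation of the diagnostic accuracy will be based on the cross-examination with the CT scan and the pathology results". The same section fixes the order of events: "All prospectively included patients with colon cancer will be preoperatively submitted to MRI for staging". The index test result thus exists before any specimen is read.

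On the reference reading itself, 3.13 says only "At the same time, the pathological assessment of the specimen will be recorded", at the one-month reassessment. It does not say who assigns the categories or with what information. Section 3.16 places patient data "both in the patient charts and in an electronic database".

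**The concern.** In a single-arm accuracy study, the readings that most need protection are those of the index test and of the reference standard. Section 3.11 is written around the patient and the treating team and protects neither. This point concerns the reference reading.

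The surgeon, whose operation yields the specimen, is openly aware of the MRI, and nothing withholds the MRI from the pathologist. If the pathologist knows it, there are two plausible routes to bias:

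- A borderline depth of invasion may be settled in the direction that the MRI suggested.
- A margin or organ surface flagged on MRI may be sampled more thoroughly than one that MRI called clear, so that infiltration missed by MRI is also missed by histology.

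Both routes raise apparent MRI accuracy. The error is systematic, so a larger sample does not reduce it. It arises when the specimen is reported, so a later statistical analysis plan cannot undo it.

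**Working it through.** **1. What the protocol settles for each role**

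- Patient, surgeon, oncologist, radiotherapist, data recorder: declared unmasked (3.11).
- Pathologist: not mentioned in 3.11. Histology is the reference in 2.1 and one of two comparators in 3.4.
- Order: MRI before surgery (3.4), pathology recorded around one month after it (3.13).
- Passage of information: no section says that the MRI report reaches the pathologist, and none says that it is withheld.

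Masking of the reference reading is therefore not secured. It is not expressly ruled out either.

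**2. The plan's own figures**

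Section 3.9 gives specificity 84% for T1/T2 versus T3/T4, alpha 5%, power 80%, d = 10%, dropout 30% and N = 120. The formula is not stated. A one-sample test of 0.84 against 0.94, two-sided, comes close:

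n = [(1.960 × √(0.84 × 0.16) + 0.842 × √(0.94 × 0.06)) / 0.10]² = 84.35, and 84.35 / 0.70 = 120.5.

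Rounding up to 85 first gives 85 / 0.70 = 121.4, that is 122. Masking does not enter this calculation, so the point changes no stated figure. The 84% and the d of 10% serve below only as a yardstick.

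**3. Illustration for T stage (assumed inputs)**

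Let A be true agreement, b the share of discordant cases that are borderline, and h the share of those settled toward MRI. Apparent agreement is A + (1 − A) × b × h. Take A = 0.84 as a stand-in, b = 0.25 to 0.75 and h = 0.25 to 0.50:

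- Low: 0.84 + 0.16 × 0.25 × 0.25 = 0.85
- High: 0.84 + 0.16 × 0.75 × 0.50 = 0.90

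The gain is 1 to 6 points, that is 10% to 60% of d.

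The 84% is a specificity, not an agreement rate, so the specificity version is worth showing. If only MRI false positives are relabelled, they leave the denominator, and apparent specificity is Sp / [1 − (1 − Sp) × b × h]:

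- Low: 0.84 / (1 − 0.16 × 0.0625) = 0.84 / 0.99 = 0.848
- High: 0.84 / (1 − 0.16 × 0.375) = 0.84 / 0.94 = 0.894

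That is a gain of about 0.8 to 5.4 points. MRI false negatives relabelled as T1/T2 would raise it further. The order of magnitude is the same.

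**4. Illustration for infiltration (assumed inputs)**

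Let s be true MRI sensitivity and q the share of infiltrations found by MRI-directed blocks that routine blocks would also find. If only MRI-positive areas receive directed blocks, apparent sensitivity is s / [s + (1 − s) × q]. With s = 0.75:

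- q = 0.9: 0.75 / (0.75 + 0.225) = 0.769
- q = 0.7: 0.75 / (0.75 + 0.175) = 0.811

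Uniform routine sampling restores 0.75q / (0.75q + 0.25q) = 0.75, but at a price. Of 100 true infiltrations, 75 are flagged by MRI, and routine blocks find 75 × 0.9 = 67.5 down to 75 × 0.7 = 52.5 of these. The other 7.5 to 22.5 would be counted as MRI false positives. This bears on the fix.

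**The case against.** The strongest reply is that 3.11 does not say what a quick reader might infer, namely that the pathologist is unmasked. Its list of open roles leaves the pathologist out, which fits a masked pathologist as well as an unaddressed one. That stands: the protocol is silent, and the point is that it fails to provide for masking.

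The routes to bias are also inferred. Borderline calls, block sampling and the content of the pathology request appear nowhere in the protocol, and b, h, q and the 75% sensitivity have no source there. That stands too: both illustrations are assumption only. For the T1/T2 versus T3/T4 split used in 3.9, moreover, only calls at the T2/T3 boundary matter. A T3/T4 call matters only for T-stage accuracy in the broader wording of 3.7.

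A reader might further infer that every endpoint is affected through the specimen. The documents do not support this. Section 3.4 cites CT beside pathology, and 3.8 includes distant nodes and peritoneal infiltration, which a resected specimen need not contain.

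Nor is it a contradiction that 3.11 leaves the data recorder unmasked while 3.15 says "Data collection and recording will be carried out by an independent, third party, researcher". Independence is not masking.

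The reply does not dispose of the point. Masking of the reference reader is a matter of trial conduct that must be in place before specimens are reported, and the one section on masking does not secure it.

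**Conclusion.** The point holds as a gap in design. As written, the main reference standard may be read with the index test result known, and this can raise the apparent accuracy of MRI for T stage and for those secondary endpoints that rest on the specimen. The protocol does not show that it will happen, and the size cannot be derived from it. Under the assumed rates in the working, the gain in agreement is roughly 1 to 6 points. The figure rests on using 84% as a stand-in for agreement and on the chosen shares of borderline and MRI-following calls. If half of all disagreements were settled toward MRI, the same formula would give 0.84 + 0.16 × 0.5 = 92%. The sample size of 120 is not called into question here.

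**What to change.** Add to 3.11 that the pathologist assigns and records the reference T, N, retroperitoneal margin and organ-infiltration categories before the study MRI findings are disclosed, and that the primary accuracy analysis uses these masked categories.

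Add also that any later MRI-directed re-sampling remains available for clinical use, is recorded separately from the first categories, and is reported in a sensitivity analysis. Without that analysis, infiltration confirmed only by directed sampling would be counted silently as an MRI false positive. With it, both results are visible. The directed result should stand beside the masked one and not replace it, because only MRI-flagged areas receive the extra sampling.

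The cost is a few sentences in the protocol and a recording step before disclosure. The small downside is that MRI-directed sampling follows the first recording. If the pathologist is already masked in practice, the change only puts that on record.

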3.7 Primary endpoint

Diagnostic accuracy in T stage. Evaluation of diagnostic accuracy in the T stage assessment
[Time Frame: 1 month postoperatively]

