3.9 Calculation of the sample size

The sample size calculation was based on the primary endpoint. According to the literature, the specificity of MRI of the T1/T2 vs T3/T4 differentiation is 84%. Therefore, for a prospective study with alpha: 5%, power: 80%, d=10% and dropout rate: 30%, the estimated number of patients is 120.

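### The data recorder is explicitly unblinded and nothing requires the imaging category to be entered before pathology is known, so late or unclear imaging entries could be coded with the pathology in view

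*Protocol*

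**What the plan says.** Protocol section 3.11 (Blindness) declares that there is no blinding of the patient, of the treating physicians "and the researcher who will record the data". It does not mention the radiologists who read the scans or the pathologist.

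Section 3.15 (Study Group) assigns the recording to one role: "Data collection and recording will be carried out by an independent, third party, researcher". It does not separate imaging records from pathology records.

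On timing, section 3.4 (Study Arms) says "All prospectively included patients with colon cancer will be preoperatively submitted to MRI for staging", but not when the resulting category is written down. Section 3.13 (Monitoring), on the reassessment one month after the operation, says "At the same time, the pathological assessment of the specimen will be recorded". Section 3.16 says that data are kept "both in the patient charts and in an electronic database", with no order of entry, lock or time stamp.

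On use, section 3.4 says "The evaluation of the diagnostic accuracy will be based on the cross-examination with the CT scan and the pathology results". The primary endpoint in section 3.7 is "Diagnostic accuracy in T stage. Evaluation of diagnostic accuracy in the T stage assessment", with a time frame of one month after surgery. Section 3.9 takes from the literature that "the specificity of MRI of the T1/T2 vs T3/T4 differentiation is 84" per cent and sizes the study on that cut.

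**The concern.** In an accuracy study the result depends on which imaging category is set against which pathological category. If the person entering the imaging category already knows the pathology, a report that does not settle between T2 and T3, or that leaves margin involvement open, can be resolved towards the known answer without any intent to do so. That raises the measured agreement at the T1/T2 versus T3/T4 boundary, and it can do so for CT as well as MRI. The secondary endpoints (nodes, retroperitoneal margin, peritoneal or organ infiltration) are open to the same effect.

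The recorder's independence, which section 3.15 relies on, guards against a stake in the result. It does not guard against knowing the answer. Masking at data capture also cannot be restored later by an analysis plan.

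**Working it through.** **1. Does the protocol allow it?** Put the sections side by side.

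- 3.11: the recorder is not blinded. This is stated, not left out.
- 3.15: that role collects and records the data, and no other recorder is named. That the role enters both imaging and pathology is an inference from this unrestricted wording.
- 3.13: pathology is recorded at one month. No entry time is given for imaging.
- 3.16: charts and a database, with no order of entry.

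Entering both categories at one month would break no rule in the document. Because the MRI is preoperative and done for staging, a clear report written at the time already fixes its category. What remains exposed is late entry and the coding of unclear reports.

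**2. The plan's own figure.** Inputs from section 3.9: 84%, alpha 5%, power 80%, d = 10%, dropout 30%, N = 120. The formula is not stated. A two-sided one-sample test of 0.84 against 0.94 gives

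n = [1.96 × √(0.84 × 0.16) + 0.842 × √(0.94 × 0.06)]² / 0.10² = 84.3,

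and 84 / 0.70 = 120 (85 / 0.70 rounds up to 122). So 120 is reproduced, with 120 × 0.70 = 84 evaluable patients. Nothing in this point changes N.

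**3. Size under assumptions.** None of these three inputs is in the protocol:

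- e, the share of patients with an equivocal report: 5% to 15%, that is 84 × 0.05 = 4.2 to 84 × 0.15 = 12.6 patients;
- half of those would be discordant with pathology if coded without it;
- f, the share of those discordant reports recoded to match: 25% to 100%.

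Gain in overall accuracy = e × 0.5 × f, in percentage points:

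| e | f = 25% | f = 50% | f = 100% |
|---|---|---|---|
| 5% | 0.6 | 1.25 | 2.5 |
| 10% | 1.25 | 2.5 | 5.0 |
| 15% | 1.9 | 3.75 | 7.5 |

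The gain does not depend on the starting value. From an assumed 0.84 it gives 0.846 to 0.915.

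**4. Yardstick.** For a proportion of 0.84 in 84 patients the 95% half-width is 1.96 × √(0.84 × 0.16 / 84) = 7.8 points. The top of the range is about as large as that; the bottom is negligible.

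**5. Why d is not the yardstick.** Section 3.9 attaches d to specificity, whose denominator is one pathological class only, and the protocol does not give that class's share. If 20–40% of the 84 were pathological T1/T2 (an assumption; 16.8 to 33.6 patients), one false-positive report recoded to match would move specificity by 1/33.6 = 3.0 to 1/16.8 = 6.0 points. This shows that specificity is sensitive to a few entries. It does not show how many would be recoded.

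**The case against.** The strongest reply is that the mechanism is not in the document. Nothing says that reports will be equivocal or that the recorder interprets them: section 3.15 gives that role collection and recording, and section 3.4 makes the stage an output of the MRI. Section 1.1 describes radiological staging first and histological confirmation afterwards. The patient chart is a second record against which a database entry could be checked. Order of entry, locks and change logs are often left to a data-management plan or case report form, which are not shown.

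Most of this stands as a limit on the point. It confines the exposure to late or unclear entries and leaves the size wholly assumed. It does not remove the point, because the unblinded recorder is the protocol's own stated choice and the sequence of the tests is not a sequence of data entry.

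A reader might also infer more than the text supports:

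- *That the recorder was left unmasked on purpose.* Section 3.11 is explicit but gives no reason, so intent cannot be read from it.
- *That accuracy will be inflated by 2.5 to 7.5 points, most of d.* That range is only the f = 100% column above, and it sets overall accuracy against a margin that belongs to specificity.
- *That the image readers or the pathologist are unblinded.* Section 3.11 does not mention them. Their masking is a separate and possibly larger question, and masking them would not settle the transcription step.

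**Conclusion.** The point holds as an uncontrolled route to bias in the primary comparison, not as a demonstrated bias. It rests on the stated lack of blinding in 3.11, the single recording role in 3.15, and the absence of any rule that puts imaging entry before pathology. The possible gain in overall accuracy, about 0.6 to 7.5 points, depends entirely on the three assumed inputs. Confidence in the size is therefore low; confidence in what the protocol permits is high. The change should be made because it is cheap and has to be in place before the data are collected.

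**What to change.** Amend sections 3.11 and 3.15 as follows:

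- The MRI and CT categories (T1/T2 versus T3/T4, N, retroperitoneal margin, peritoneal or organ infiltration) are entered in the existing electronic database from the imaging report, then locked with a time stamp before the operation.
- Pathology is entered afterwards, in a separate form.
- Any later change to an imaging entry is logged, and the locked value is the one analysed.

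The cost is data entry in two sittings and, possibly, slightly less favourable measured accuracy. No extra staff, image reads or patients are needed, and N stays at 120.

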3.12 Exit criteria

The patient will be discharged when it is ensured that is medically safe to be released. The exit time will be regarded as the time that the patient will fulfill the Clinical Discharge Criteria. More specifically, the patient should display the following: steady vital signs, fully oriented, without nausea or vomiting, mobilized with a steady gait and without a notable bleeding.

3.13 Monitoring

Following hospital discharge, the patient will be called for reassessment at one month after the operation. Patients will be included in the standard monitoring protocol (CT, MRI, cancer markers),

unless otherwise required. At the same time, the pathological assessment of the specimen will be recorded.

3.14 Medication

Both preoperative and postoperative patient treatment will be standardized. The principles of the ERAS protocols will be applied to patients. More specifically, antimicrobial prophylaxis will include the administration of intravenous antibiotics within 60 minutes prior to the onset of operation. Patients will receive preoperative, mechanical bowel preparation and per-os antimicrobial prophylaxis. Prior to surgery, patients will abstain from solid and liquid foods for 6 and 2 hours, respectively. The nasogastric tube will be removed postoperatively and repositioned only in case of ileus. Postoperative analgesia will include a multidisciplinary approach using analgesics (paracetamol, lornoxicam) in combination with dorsal or epidural analgesia. Opioid administration will be avoided. Postoperative nausea and vomiting prophylaxis will include granisetron 3mg / 3ml IV. Mechanical and pharmaceutical thromboprophylaxis will be used. A zero-balance approach to fluid losses will be applied. Mobilization will be initiated from the first postoperative day. Feeding will be initiated on the basis of the intestinal function recovery.

3.15 Study Group

All participating members have years of experience in their field and have, therefore, completed the learning curve for the required techniques. Data collection and recording will be carried out by an independent, third party, researcher.

3.16 Conducting a Study

The study will be conducted in the Department of Surgery of University Hospital of Larissa in collaboration with the Radiology Department of University Hospital. Patient data will be recorded

both in the patient charts and in an electronic database. The required laboratory examinations will be defrayed by the patient insurance funds.

